7.3 LOST TO FOLLOW-UP

N/A

8 STUDY ASSESSMENTS AND PROCEDURES

8.1 EFFICACY ASSESSMENTS

Rating

All assessments will be performed by trained raters.

Time frame

Screening procedures / evaluation must be done on the same day or the day before inclusion of the patient into the study. The reason for this is that we assess rTMS effect independently of potentially influencing antipsychotic medication effects. Therefore, patients cannot start with antipsychotic medication treatment parallel to the rTMS treatment. Clinical interviews will be conducted by trained staff.

Imaging

MRI acquisition will consist of the following: On the day of imaging, the patient will be transported to the North Shore University Hospital 3T Siemens Prisma MRI suite. The patient will undergo an approximately 55 minutes long acquisition session. All subjects will receive structural (e.g., T1) and functional (e.g. resting BOLD fMRI, DTI, and ASL) MRI exams. During the anatomical images, the participating subject will be asked not to move, during resting state fMRI, the subject will be asked to open their eyes and to think of nothing in particular, but to stay awake. The total scanning time will be approximately 55 minutes.

Assessment of instruments

The primary outcome measure is the improvement of AVH measured with the HCS.

The secondary outcome measures are:

- Qualitative outcome of the BAVQ-R
- AVH as part of positive symptoms measured with the respective BPRS-subscale
- Global functioning assessed using the CGI and GAF
- Cognitive functioning assessed using the rBANS

Structural and functional neurophysiological characteristics are investigated as predictors for rTMS treatment response.

Outcome criteria

Responder criteria:

- a. Clinically significant improvement is defined as a score of <8 on the HCS (Hoffman et al., 2013)
- b. Drop-outs: defined as patients who discontinue treatment before completing the 4 rTMS sessions.

Premature exits:

- a. Consent for study participation is withdrawn before 4 rTMS treatments have been administered, or
- b. rTMS is discontinued for clinical or other reasons before 4 rTMS have been administered, or
- c. Patient misses more than two treatments in total.

Both drop-outs and premature exits in this study will be analyzed as last observation carried forward.

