1 PROTOCOL SUMMARY

1.1 SYNOPSIS

Title: Boost rTMS for AVH – Therapeutic Response and Neurobiological Prediction Markers in Auditory Verbal Hallucinations

Study Description: This is a randomized, placebo controlled, double-blind clinical trial. We aim to examine the efficacy of repeated transcranial magnetic stimulation (rTMS) for the treatment of auditory verbal hallucinations (AVH) in patients with schizophrenia who are not taking antipsychotic medication. We employ a novel, accelerated protocol with only 4 sessions of low-frequency rTMS in one day. The effects of this accelerated protocol will be compared to the sham stimulation. Additionally, we will examine the effects of rTMS on a neurophysiological level by evaluation mechanism of action in the temporo-parietal lobe.

Objectives: Primary Objective:
Examine the efficacy of low-frequency rTMS for AVH in patients with a schizophrenia spectrum disorder.

Secondary Objectives:
Examine the effects of rTMS on the quality of AVH, positive symptoms, general psychopathology, and the global level of functioning of these patients. Last, confirm that rTMS has no side effects on cognitive functioning.

Determine the neuroimaging-related biomarkers associated with response to rTMS using the baseline imaging parameters (rCBF, resting fMRI, T1, and DTI) to predict response to rTMS treatment. Further,

compare pre- and post-treatment imaging parameters (rCBF, resting fMRI, T1, and DTI) to characterize rTMS effects on AVH.

Endpoints:

Primary Endpoint:

- AVH assessed using the Hallucination Change Scale (HCS) at baseline (first visit), after the last TMS session, after the post-MRI.

Secondary Endpoints:

- a) Assessment of the qualitative content of hallucinations will be assessed using the revised Beliefs About Voices Questionnaire (BAVQ-R)
- b) Assessment of AVH as part of positive symptoms will be assessed with the Brief Psychiatric Rating Scale (BPRS)-subscale that includes "Hallucinatory Behavior", "Conceptual Disorganization", "Suspiciousness", and "Unusual Thought Content".
- c) Global functioning will be assessed using the Clinical Global Impression (CGI) and General Assessment of Functioning (GAF) questionnaires.
- d) Cognitive functioning will be assessed using the Repeatable Battery for the Assessment of Neuropsychological Status (rBANS).

Neurophysiological changes using magnetic resonance imaging (MRI) are investigated as predictors for rTMS treatment response.

Study Population:

N = 40

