Payne, Rushmore, Lomber, & Pascual-Leone, 2005; Wagner, Valero-Cabré, & Pascual-Leone, 2007). In most studies, rTMS is applied over the course of several days causing short-term modulations of the target region and its connected network (Maeda, Keenan, Tormos, Topka, & Pascual-Leone, 2000; Valero-Cabré, Pascual-Leone, & Coubard, 2011). Low-frequency (LF) rTMS (1 pulse/second, 1 Hz) is thought to inhibit cortical excitability in the stimulated area. This effect depends not only on the stimulation frequency, but also on the time between pulses and other influencing factors (Lefaucheur et al., 2014).

In schizophrenia, Hoffman et al. (1999) were the first to introduce rTMS for the treatment of refractory AVH in treatment-resistant patients. The authors used LF rTMS over the left temporo-parietal junction (TPJ) and showed significantly reduced AVH severity with effects lasting up to 15 weeks. The TPJ is a sensory-motor integration area and is involved in the perception of speech (Benson et al., 2001; Fiez, Raichle, Balota, Tallal, & Petersen, 1996). The increased activity found in this region during AVH (S. S. Shergill, Bullmore, Simmons, Murray, & McGuire, 2000; Silbersweig et al., 1995) may arise from deficits in self-monitoring that, subsequently, lead to misinterpretation of inner speech (Frith, Friston, Liddle, & Frackowiak, 1992; Waters, 2012).

Since the first promising rTMS trials of Hoffman et al. (1999), many studies have used the classical LF stimulation pattern delivered to the left TPJ. Regarding this, meta-analyses (Aleman et al., 2007; Demeulemeester et al., 2012; Freitas et al., 2009; C. W. Slotema et al., 2014; C. W. Slotema et al., 2010; Tranulis et al., 2008) found significant effect sizes ranging from 0.42 to 1.04 which indicate a medium to large therapeutic effect of rTMS for the treatment of AVH.

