3 OBJECTIVES AND ENDPOINTS

OBJECTIVES	ENDPOINTS	JUSTIFICATION FOR ENDPOINTS
Primary		
Examine the efficacy of low-frequency rTMS for the treatment of AVH in patients with a schizophrenia spectrum disorder.	Our primary outcome will be the score of the Hallucination Change Scale (HCS) (Hoffman et al., 2003). Response criteria: a) Clinically significant improvement in AVH is	The HCS is used as our primary outcome measure. The scale will be anchored at baseline using the narrative description of AVHs provided by the patient for the prior 24 hours, which will be assigned a score of 10. For subsequent assessments, the HCS ranges from 0-20 (with a score of 20

OBJECTIVES	ENDPOINTS	JUSTIFICATION FOR ENDPOINTS
	defined as a score of <8 on the HCS (Hoffman et al., 2013) b) Drop-outs: defined as patients who discontinue treatment before completing the 4 rTMS sessions.	corresponding to hallucinations twice as severe as baseline) (Hoffman et al., 2003; Hoffman et al., 2013). The HCS is a frequently used assessment for AVH in schizophrenia (Hoffman et al., 2003; Hoffman et al., 2013; Philipp Homan et al., 2011; P Homan et al., 2012). It is a feasible and time-efficient measure to assess severity of AVH on a daily basis and to evaluate improvement of AVH severity.
Secondary		
Monitor qualitative changes in AVH during the course of the rTMS treatment.	a) the qualitative content of AVH are assessed using the BAVQ-R to monitor changes in the content of AVH.	The BAVQ-R (CHADWICK, LEES, & BIRCHWOOD, 2000) is a self-report measure of patient's beliefs, emotions and behavior about AVH. This allows to assess changes in the quality of AVH over time and monitor if severity increases to the point of being dangerous for the patient or others (suicidal or homicidal tendencies).
Assessment of AVH as part of positive symptoms.	b) positive symptoms BPRS-subscale including "Hallucinatory Behavior", "Conceptual Disorganization", "Suspiciousness", and "Unusual Thought Content".	The positive symptoms BPRS-subscale is a well validated, often in studies used measure to assess positive symptoms including AVH (Robinson et al., 2015; Shafer, 2005).

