Precautions to minimize MR risks have been described above. Briefly, disposable earplugs or non-magnetic headphone sets will be used for all participants to minimize the risk associated with acoustic noise levels. To minimize risks related to the magnetic field, our facility incorporates a complete range of procedures to assure security of the restricted access area, and careful screening of potential subjects, before they enter the restricted access area. The system will be operated within limits already determined not to pose significant risk to humans. Proper and routine monitoring of all radio frequency electronics (e.g. coils, transmitters, system security, etc.) will be performed on a regular basis to minimize the risks associated with Specific Absorption Rate (SAR). Incidental risks are minimized by an extensive set of safety checks employed by our facility prior to scanning. Claustrophobia from magnetic resonance imaging will be reduced by explaining the nature of the scanner in detail to all participants prior to enrollment and allowing them to become acclimated to the procedure by using a mock scanner. Subjects who have a history of significant claustrophobia will not be entered into the study and if it occurs, the study will be terminated at the subject's request. All subjects undergoing MR imaging will be provided with a "squeeze ball" that will alert the operator when the subject has a problem that needs to be addressed or wants to terminate the exam.

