9.4.3 ANALYSIS OF THE SECONDARY ENDPOINT(S)

Our secondary goal is to test if rTMS improves also the quality of AVH (BAVQ-R), positive symptoms (BPRS-subscale), general psychopathology (CGI), and global functioning (GAF). Further, we want to confirm that rTMS has no impact on cognitive functions (rBANS).

Therefore, we will compute a number of repeated ANCOVAs with time of measurements as the within-subject factor, group (treatment vs. placebo) as between subject's factor, and baseline BAVQ-R scores, the positive symptom BPRS-scale, the CGI, and GAF scores as covariates, respectively. Patients who drop out of the study will not be included in the analyses. Further, we will compare the rBANS scores of baseline with the outcome scores within patients.

Additionally, we want to test if baseline neuroimaging biomarkers can predict response to rTMS. Therefore, voxel-wise multiple regression analyses in our neuroimaging measures will be performed to reveal areas and networks which correlate with the baseline scores of the HCS. We will calculate structural and functional connectivity analyses.

Preprocessing, and overview of the neuroimaging measures:

Baseline metabolic neuronal activity

The treatment effect will be monitored by assessing the baseline resting metabolic neuronal activity measured by ASL (Philipp Homan et al., 2011; Kindler et al., 2012; Orosz et al., 2012). Additionally, variations in resting CBF may be used as covariates of nuisance in all the analysis steps described so far.

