To investigate the structural properties of GM and WM the 3D structural T1 and DTI measurements will be used. T1 images will be used to define the regions of interest (ROI) for both structural and functional connectivity analyses. The ROIs will comprise cortical regions in the STG and superior temporal sulcus (STS, Brodmann areas/BA 41, 42 and 52) and in the subcortical thalamic area (medial geniculate body of thalamus/MGB).

With regard to structural connectivity analyses, diffusion tensor images will be used to compute fractional anisotropy (FA) values for further use in a voxel-wise statistical analysis, which will be conducted using Tract-Based Spatial Statistics (TBSS) (Smith et al., 2006); part of FSL (Smith et al., 2004) (version 5.0). FA maps are created by fitting a tensor model to the raw diffusion data using the FMRIB diffusion toolbox. Subsequently, a brain extraction tool will remove all non-brain parts of the image (Smith, 2002). All subjects’ FA data will be coregistered to a 1 mm × 1 mm × 1 mm Montreal Neurological Institute (MNI) standard space. This step will be performed using a non-linear registration tool FNIRT (FMRIB’s Non-Linear Image Registration Tool), which uses a B-spline representation of the registration warp field (Rueckert et al., 1999). Additionally, a mean FA image will be created and thinned in order to create a mean FA skeleton that represented the centers of all tracts common to the group. A lower FA threshold of 0.2 will be used to prevent the inclusion of non-skeletal voxels (Smith et al., 2006). Each subject’s aligned FA data will then be projected onto this skeleton. The resulting data will be analyzed using voxel-wise cross-subject statistics including a randomization tool, which is a simple permutation program that allows modeling and inferences within the framework of GLM-setup and is based on non-parametric inference methods (Nichols & Holmes, 2002).

Concerning functional connectivity analyses, the ROIs will be used as seed regions to compute the functional connectivity from these regions to other cortical brain regions using the Conn toolbox, a MATLAB-based cross-platform mapping software (www.nitrc.org/projects/conn). Further, GM analyses will be performed using voxel-based morphometry (VBM) (Good et al., 2001). VBM will be computed within the statistical parametric mapping (SPM8: <http://www.fil.ion.ucl.ac.uk/spm/>). Cortical thickness will be estimated using FreeSurfer (<http://surfer.nmr.mgh.harvard.edu>).

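### The protocol describes no record of whether patients heard voices during the resting BOLD and ASL runs, which limits what the functional predictors and within-arm pre/post changes can show

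*Combined protocol and SAP*

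**What the plan says.** The only instruction for the functional runs is in Section 8.1: "during resting state fMRI, the subject will be asked to open their eyes and to think of nothing in particular, but to stay awake". Nothing specific is said for the ASL run. The squeeze ball in Section 8.2 "will alert the operator when the subject has a problem that needs to be addressed or wants to terminate the exam"; it is not a way to signal voices.

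Hallucinations are rated on the HCS. The Synopsis gives the times: "AVH assessed using the Hallucination Change Scale (HCS) at baseline (first visit), after the last TMS session, after the post-MRI". Section 3 anchors the baseline "using the narrative description of AVHs provided by the patient for the prior 24 hours" and gives every patient a score of 10.

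The imaging has two uses. Section 9.4.3 says "we want to test if baseline neuroimaging biomarkers can predict response to rTMS", which is hypothesis 6 in Section 9.1. The Synopsis also plans to "compare pre- and post-treatment imaging parameters (rCBF, resting fMRI, T1, and DTI) to characterize rTMS effects on AVH". On regions, Section 9.4.3 states: "The ROIs will comprise cortical regions in the STG and superior temporal sulcus". The only nuisance covariate it names for imaging is variation in resting CBF, and that is optional.

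**The concern.** The Synopsis recruits patients because they are currently hearing voices. Section 2.1 explains the choice of target partly by "The increased activity found in this region during AVH", meaning the temporo-parietal junction. On that premise, a resting blood-flow or network value in or near this region depends in part on whether the patient happened to hear voices in those minutes.

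Two conclusions are at stake. For prediction, voices that come and go by chance add noise to the marker and weaken a true association with response. If voices in the scanner track current illness activity, the marker may partly stand in for current symptoms. For the pre/post aim, a fall in blood flow within the real-rTMS arm could be a lasting neural change or simply fewer voices during the second scan.

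The plan already standardises other momentary states: Section 5.3 bars nicotine and caffeine for 2 hours before each scan. It describes nothing for the state closest to its own question.

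**Working it through.** **Is the information available elsewhere?** The candidate sources in the protocol are:

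- Baseline HCS: 10 for everyone, anchored on the prior 24 hours. A constant cannot separate patients who heard voices in the first scan from those who did not.
- HCS after the post-MRI: it rates severity against baseline, has no stated recall window, is not tied to the BOLD or ASL run, and has no counterpart after the first scan.
- BAVQ-R (Section 2.2.1, every visit): content, severity and distress of voices, not the scan minutes.
- Squeeze device and microphone (Sections 2.2.1 and 8.2): for discomfort, problems or stopping.
- Schedule of Activities (1.3), imaging text (8.1) and analysis text (9.4.3): no in-scan or post-run item on voices.

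**The plan's own figure.** The documents give no number for the imaging aims. Section 9.2 gives 20 per arm for the primary comparison (effect size 0.9, 80% power, 5%). A two-sided two-sample t-test needs 20.39 per arm, and power at 20 is 0.792, so the figure essentially reproduces. It is used here only for n = 20 in the real arm.

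**Prediction, illustration only.** Assume a true correlation ρ between marker and response, and let a share s of the marker's between-patient variance be momentary state unrelated to response. Then

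observed r = ρ × √(1 − s), and power ≈ Φ(atanh(r) × √(n − 3) − 1.96).

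For ρ = 0.6, s = 0, n = 20: atanh(0.6) = 0.693; 0.693 × √17 = 2.858; 2.858 − 1.96 = 0.898; Φ(0.898) = 0.815. For s = 0.5: r = 0.424; 0.453 × 4.123 = 1.867; Φ(−0.093) = 0.463.

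| State share s | r (ρ = 0.5) | Power | r (ρ = 0.6) | Power |
|---|---|---|---|---|
| 0 | 0.50 | 62% | 0.60 | 82% |
| 0.10 | 0.47 | 57% | 0.57 | 76% |
| 0.25 | 0.43 | 48% | 0.52 | 66% |
| 0.50 | 0.35 | 33% | 0.42 | 46% |

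These are for a single test. Section 9.4.3 plans voxel-wise regressions, to which they do not carry over directly.

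**Pre/post, illustration only.** Assume voices raise regional CBF by d = 0.5 to 1.0 SD, and are present in 60% of first scans in both arms, in 50% of second scans on sham and in 20–40% on real rTMS.

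- Real-arm change from state alone = d × (second-scan share − 0.60): from 0.5 × (0.40 − 0.60) = −0.10 SD to 1.0 × (0.20 − 0.60) = −0.40 SD.
- Difference between arms in change from state alone = d × (real share − sham share): from 0.5 × (0.40 − 0.50) = −0.05 SD to 1.0 × (0.20 − 0.50) = −0.30 SD.

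**The case against.** A reader might infer that in-scan voices are never recorded in this trial. The documents do not show that. CRFs are completed at every visit (Section 1.3) and a Manual of Procedures is cited (Section 10.1.10), but neither is available here. What can be said is that the protocol describes no such record.

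A reader might also infer that the real-versus-sham comparison of imaging change is confounded. It is not. Randomisation balances the first-scan state in expectation, and fewer voices at the second scan is then a consequence of treatment, so the arm contrast remains a valid total effect. What is lost is the ability to say how much of it runs through voices during the scan. Within-arm contrasts lack that protection; the t-test of rest and TMS conditions in Section 9.4.3 appears to be one.

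A third tempting reading is that a state-dependent predictor is spurious and must be adjusted. Hypothesis 6 asks only whether markers predict response. A marker that partly reflects current symptoms can still predict, and if in-scan voices carry response-relevant information, compulsory adjustment removes signal. The reference list includes, by title, work describing tonic hyperactivity in the left superior temporal gyrus as a possible trait marker. The documents do not settle state against trait.

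Finally, neither the correlation nor the state share comes from the documents. At ρ = 0.6, a share of 5% or 10% lowers power only from 82% to 79% or 76%; at ρ = 0.4, power is 42% before any state variance. This stands: the power figures are a range under assumptions, not an estimate.

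**Conclusion.** The point holds as a gap in the secondary imaging aims. The protocol describes no rating of voices tied to the resting BOLD or ASL runs, and no listed measure can stand in for one. By the protocol's own premise, momentary voices may add noise to, or partly explain, a functional predictor. Within-arm pre/post changes in blood flow or networks cannot be separated from fewer voices during the second scan.

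The size cannot be derived from the documents. Under the stated assumptions (n = 20, ρ = 0.5 to 0.6, one two-sided 5% test), the loss runs from none to a fall from 62–82% to 33–46% power. That range assumes state unrelated to response; state related to severity or response could inflate an association instead.

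The structural measures (T1, DTI), the primary HCS comparison and its sample size are unaffected. This is an inexpensive improvement, worth making because the information cannot be recovered after the scan.

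**What to change.** In Section 8.1, once both the resting BOLD and ASL runs are finished at each scan, ask whether voices were heard in each run and for roughly what share of it, and enter the answers on the CRF. Ask after both runs, not between them, so that the question does not draw attention to voices in the next run. The microphone in the bore (Section 2.2.1) suffices.

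In Section 9.4.3:

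- Report the baseline predictor models with and without baseline in-scan voices as a covariate, as a sensitivity analysis.
- Use HCS response as the outcome. The text correlates imaging with baseline HCS, which is 10 for everyone; no covariate can help a model with a constant outcome.
- Report in-scan voices by arm at both scans beside the pre/post contrasts. Do not adjust the treatment contrast for the post-treatment rating, except in an analysis labelled as mediation or sensitivity.

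The cost is about a minute per scan, one CRF entry and one degree of freedom. At ρ = 0.6 with no state variance, that degree of freedom lowers power from 81.5% to about 79% (0.693 × √16 − 1.96 = 0.81). The rating is retrospective self-report, so it would capture only part of any state variance, and asking at the first scan may prime patients at the second.

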8.2 SAFETY AND OTHER ASSESSMENTS

TMS

The treatment will be offered only if clinically indicated and the benefits of procedure outweigh risks. Therefore, participating in the study does not introduce additional risks to the patient other than the risks which are already present because of the clinical care. rTMS is a non-invasive procedure with the most common side effect being headache or pain, which is transient and responds well to combination of acetaminophen and ibuprofen (we will administer if patients require so). If local scalp pain or face muscle pain occurs, adjustment of the coil usually alleviates the pain. There are no known mechanisms through which the induced magnetic field produced during TMS stimulation could generate biological adverse effects in the absence of extraneous implanted metal in the skull or brain. That is the reason we will exclude all patients with metal implants (they would not be eligible because of the MRI component either). The most significant safety concern is seizure, however, as can be seen from Table 3, 1Hz rTMS for 1800 seconds is considered safe (Rossi et al., 2009). As a safety precaution, however, we will exclude patients with seizure disorders from this study. There are no additional significant risks due to study procedures.

MRI

Precautions to minimize MR risks have been described above. Briefly, disposable earplugs or non-magnetic headphone sets will be used for all participants to minimize the risk associated with acoustic noise levels. To minimize risks related to the magnetic field, our facility incorporates a complete range of procedures to assure security of the restricted access area, and careful screening of potential subjects, before they enter the restricted access area. The system will be operated within limits already determined not to pose significant risk to humans. Proper and routine monitoring of all radio frequency electronics (e.g. coils, transmitters, system security, etc.) will be performed on a regular basis to minimize the risks associated with Specific Absorption Rate (SAR). Incidental risks are minimized by an extensive set of safety checks employed by our facility prior to scanning. Claustrophobia from magnetic resonance imaging will be reduced by explaining the nature of the scanner in detail to all participants prior to enrollment and allowing them to become acclimated to the procedure by using a mock scanner. Subjects who have a history of significant claustrophobia will not be entered into the study and if it occurs, the study will be terminated at the subject's request. All subjects undergoing MR imaging will be provided with a "squeeze ball" that will alert the operator when the subject has a problem that needs to be addressed or wants to terminate the exam.

